## VI. Criteria for Subject Termination

- Subject attempts suicide or seriously deteriorates; if so, appropriate care will be provided.
- Develops serious complications of an ulcer, such as gastrointestinal bleeding, perforation, or obstruction.
- Engages in behaviors or develops any condition that the PI deems makes it medically unsafe or inappropriate to remain in the study.

## STUDY TREATMENTS AND COMPLIANCE

Subjects who meet the eligibility criteria will receive one week of single-blinded escitalopram placebo + single-blinded celecoxib placebo. Subjects who continue to meet eligibility at randomization will receive open-label escitalopram (beginning at 10mg/day) + double-blinded treatment of celecoxib (fixed at 400mg/day) or placebo. Escitalopram doses may be optimized based on efficacy and tolerability over the 8 weeks of active treatment. Subjects will be randomized according to a fixed assignment ratio of 1:1 (escitalopram + celecoxib: escitalopram + placebo). Assignment to groups is based on a pharmacy generated randomization code.

### I. Compliance

To ensure compliance, participants be asked to return all unused medication at the following visit. The returned capsules will be counted. Additionally, blood concentrations of escitalopram and celecoxib will be determined at Baseline, Week 4 and Week 8.

### II. Procurement of Compounds

Escitalopram and celecoxib will be purchased from the pharmaceutical companies that market them. In the US celecoxib is marketed by Pfizer and escitalopram is marketed by Forest Laboratories. The pharmacy will produce placebo identical in appearance to celecoxib and escitalopram.

## STUDY PROCEDURES

### Schedule of Events

Procedure	Screen 1	Screen 2	Baseline	Week 1	Week 2	Week 4	Week 8
Consent	X						
Assign Subject ID	X						
MINI	X						
HAM-D/HAM-A/MADRS	X*	X*	X	X	X	X	X
CGI/CSSRS/AdverseEvents/CSULGIE	X		X	X	X	X	X
Self-Assessment Packet			X	X	X	X	X
Dispense Study Medication		PBO	X	X	X	X	X
Physical Exam	X						X
Drug Screen and Pregnancy Test	X						X
Routine Clinical Labs	X						X
Research Blood Draw			X			X	X
CBC/PT/PTT Monitoring	X				X	X	X
Pulse Wave Analysis			X			X	X

Heart Rate Variability			X			X
Albuterol Challenge			X			X
Pulse Wave Velocity			X			X
Saliva Sampling		X	X	X	X	X

\*HAM-D only.

Routine Clinical Labs include complete blood count, complete metabolic panel, lipid profile and thyroid function.

The following assessments are included in the self-assessment packet:

- Beck Depression Inventory (BDI)
- Beck Anxiety Inventory (BAI)
- State/Trait Anxiety Inventory (STAI)
- Spielberger Anger Expression Inventory (STAXI)
- International Physical Activity Questionnaire (I-PAQ)
- Quality of Life and Enjoyment Questionnaire (QLES-Q)
- The Short-Form McGill Pain Inventory (MPI)
- Perceived Stress Scale (PSS-14)

Subjects will be treated as outpatients for a total of ten weeks. Subjects must complete at least six weeks to be regarded as completers. If a subject chooses to withdraw from the study on or after six weeks of treatment, he or she will be asked to complete end-of-study assessments at that time. Those results will be carried forward for the purpose of data analysis.

Subjects will not receive any other type of therapeutic intervention (e.g., psychotherapy) during participation in the study. Such options may be offered to them at the conclusion of the study, if appropriate.

Subjects who complete the study and respond favorably will remain under the care of the LUMC physician, if they wish.

## ASSESSMENTS

### I. Psychometric Data Collection Instruments

Mini International Neuropsychiatric Interview (MINI)

Hamilton Rating Scales for Depression (HAM-D) and Anxiety (HAM-A)

Beck Depression Inventory (BDI); Beck Anxiety Inventory (BAI)

MADRS-Montgomery Asberg Depression Rating Scale (MADRS)

Columbia Suicide Severity Rating Scale (C-SSRS)

State/Trait Anxiety Inventory (STAI)

Spielberger Anger Expression Inventory (STAXI)

Inventory of Clinically Significant Upper and Lower GI events (CSULGIE)

Short-Form McGill Pain Inventory (MPI)

Perceived Stress Scale (PSS-14)

Quality of Life and Enjoyment Questionnaire (QLES-Q)

International Physical Activity Questionnaire (IPAQ)

## II. Blood Sampling

Blood samples will be drawn at trough levels after instructing subjects to ensure a 12-hour interval after the last dose in the evening preceding the morning blood draw. Plasma, serum and buffy coat will be immediately separated and frozen at -80°C for future analysis.

### Measurement of Plasma Pro-Inflammatory Biomarkers

These measures will be obtained from blood drawn at Baseline, Week 4 and Week 8 using the Randox Technologies “Evidence InvestigatorTM” system. This compact Biochip array system is comprised of a super-cooled Charge Coupled Device (CCD) camera and unique image processing software. This Biochip technology has been validated using blood samples from our preliminary studies. Several cytokines, chemokines and growth factors can be analyzed simultaneously using microliter volumes of plasma. The results produced by the Biochips are impressive and comparable to results obtained by individual ELISAs for each parameter. This assay will be completed in an LUMC lab.

### Measurement of Serum Kynurenines and the Tryptophan Pathway

These measures will be obtained from blood drawn at Baseline, Week 4 and Week 8. The measurement of tryptophan and kynurenines has been established in the Psychoneuroimmunology (PNI) Laboratory of the Psychiatric Hospital of LMU, Munich using Ultra Performance Liquid Chromatography – Mass Spectrometry (UPLC-MS) methodology. The method has been standardized by the participation of 6 universities in the External Quality Assurance Scheme as a part of the EU collaboration project MOODINFLAME. The measured metabolites are: tryptophan, kynurene, kynurenic acid, 3-hydroxykynurene, 3-hydroxyanthranilic acid and quinolinic acid. This assay will be completed by collaborating investigators in Munich, Germany.

### Measurement of Blood Levels of Celecoxib and Escitalopram

These measures will be obtained from blood drawn at Baseline, Week 4 and Week 8. Plasma concentrations of celecoxib and escitalopram will be measured using a solid phase HPLC method. This measurement will help the study team determine whether subjects are compliant, adequately dosed and if celecoxib changes escitalopram blood levels, or vice versa. Celecoxib levels will be assayed by collaborating investigators in Munich, Germany. Escitalopram levels will be assayed by collaborating investigators in Charleston, SC.

### Measurement of COX-2 Inhibitory Level in Blood via PGE2 Activity

These measures will be obtained from blood drawn at Baseline, Week 4 and Week 8 using an EIA kit from Cayman Chemical Inc. This fast and reliable method uses LipoPolySaccharide (LPS) stimulation and a special Cremophor EL-EtOH vehicle to solubilize and assay PGE2. The method is rapid and eliminates COX-1 activity artifact using aspirin and an available thromboxane synthase inhibitor (TXBSI). This assay will be completed in an LUMC lab.

### Monitoring of Possibility of Bleeding Diathesis

These measures will be obtained from blood drawn at Week 2, Week 4, and Week 8. Since the combination of an SSRI and a COX-2 inhibitor has the potential to induce bleeding diathesis, a complete blood count (CBC), prothrombin time (PT) and partial thromboplastin time (PTT) will be evaluated. Prothrombin Time and aPTT testing are performed on the Sysmex CA-7000 analyzer utilizing the scattered light detection method. The analyzer irradiates red light (660 nm) onto a mixture of blood plasma and reagent and detects the change in turbidity (when the fibrinogen is transformed into fibrin) as the change in scattered light. A curve is generated, plotting time against the amount of scattered light. This sample will be processed by LUMC Clinical Laboratories.

## III. SphygmoCor® Assessments

All SphygmoCor® measures will be obtained using the non-invasive SphygmoCor® device (SCOR-Vx, AtCor Medical Pty, Ltd) equipped with the most recent software (v9.0, AtCor Medical, West Ryde, Australia). Brachial blood pressure will be recorded at the same session using a standard method.

#### Pulse Wave Analysis to Quantify Arterial Stiffness

Subjects will undergo the Pulse Wave Analysis at Baseline, Week 4 and Week 8. Pulse-wave analysis (PWA) is a non-invasive, FDA-approved technique that allows for the assessment of arterial stiffness. Pulse wave measurements have been established as prognostic markers of cardiovascular morbidity and mortality (Papaioannou et al, 2007; Weber et al, 2007). These wave indices may also serve as prognostic markers of response to therapy (Weber et al, 2007; Williams et al, 2006). A portable tonometric probe is positioned over the maximal arterial pulse of the artery under study. A minimum of twenty sequential pressure waveforms must be recorded. SphygmoCor® Software generates mean peripheral and corresponding central and aortic pressure waveforms using a validated transfer function. Intra- and inter- observer reproducibility of these measures has been established in various populations (Papaioannou et al, 2007; Wilkinson et al, 2002). Resting wave form will be recorded using standard PWA technique, as described by Nutt et al (2006) and Rybakowski et al (2006).

#### Albuterol Challenge to Assess Endothelial Function

Subjects will undergo the Albuterol Challenge at Baseline and Week 8 to assess endothelium-dependent vasodilation. Albuterol (2 x 200µg) will be given by inhalation with a spacer device. The subject will be asked to slowly inhale for 50 seconds, and then hold breath for 10 seconds. After a 30 second rest, the procedure will be repeated. Albuterol induces vasodilation by way of receptors on the endothelium through a nitric oxide pathway (Hayward et al, 2002; Wilkinson et al, 2002). Pulse Wave Analysis will be performed at 0, 5, 10 and 15 minutes after albuterol treatment. Responses to the Albuterol Challenge will be defined as the maximum possible difference between Baseline augmentation index and post-treatment augmentation index.

#### Pulse Wave Velocity

Subjects will undergo the Pulse Wave Velocity assessment at Baseline and Week 8. The assessment involves the measurement of pulse waves at the common carotid artery and on the femoral artery using the aforementioned probe. A 3-lead ECG will be used to simultaneously obtain heart rate values. ECG recording during measurements is necessary for synchronization of carotid and femoral pulse wave times. The distance from the sternal notch to the femoral location and from sternal notch to the carotid location are measured manually and entered into the program, transit time between carotid and femoral pressure waves is calculated and Pulse Wave Velocity is PWV computed by the software.

#### Heart Rate Variability

Subjects will undergo the Heart Rate Variability assessment at Baseline and Week 8. This technique allows for the assessment of sympathetic/parasympathetic imbalance in depression, which may be central to the development of cardiovascular disease secondary to depression. HRV is a natural physiological function of a healthy heart capable of responding and adapting to changing demands of life circumstances.

### **IV. Safety Assessments and Adverse Events Monitoring**

A complete physical examination with clinical laboratory assessments will be performed at enrollment and termination. Bleeding diathesis monitoring will be completed with higher frequency, as outlined in the schedule of events. Any negative clinically significant changes from the entry examination will be recorded as adverse events.

Adverse event (AE) monitoring will formally occur after weeks 1, 2, 4, and 8 of treatment. Subjects will be asked to describe health concerns since the last visit. Suicidality will be assessed at each visit by direct questioning and the Columbia Suicide Severity Rating Scale (C-SSRS).

All adverse events will be monitored until stable regardless of when the event takes place. If the event occurs at the end of the study, it will be referred to the subject's primary care physician and/or psychiatrist for continued treatment and/or follow-up.

## **ADVERSE EVENTS REPORTING**

All AEs will be reported, regardless of whether the event seems related to the study drugs escitalopram and/or celecoxib. Study staff will also report AEs spontaneously reported by the patient and/or observed by the staff. Information that will be collected includes:

- A description of the event
- Start and stop date
- Action taken with regards to investigational product
- Outcome
- If the AE causes the patient to discontinue the study
- A statement reporting if the AE meets criteria for a Serious Adverse Event or not (see below)
- The investigator's assessment of the causal relationship between the event and the study drug
- Intensity of the AE
  - mild (awareness of sign or symptom, but easily tolerated)
  - moderate (discomfort sufficient to cause interference with normal activities)
  - severe (incapacitating, with inability to perform normal activities)

All serious adverse events (SAE) will be documented and reported to appropriate regulatory bodies. All adverse events will be summarized in a report at intervals requested by the IRB and the Data Safety Monitoring Board.

## **ETHICS AND EVALUATION OF RISKS**

### **I. Consent Process Overview**

Each subject will be presented the Informed Consent Form after meeting criteria for inclusion. Subjects will be asked to read the Informed Consent Form carefully. Subjects will be told about the effects of celecoxib and escitalopram. Subjects will be told that their participation in this study could benefit patients with BPD in the future. Subjects will also be informed of potential risks and discomforts. Any subject who appears incapable of providing informed consent (e.g., due to cognitive impairment) will not be enrolled. Subjects will be informed that they can decline to participate in the study without penalty or loss of treatment. Subjects will also be informed may withdraw from the study prior to analysis of their data. Following a thorough resolution of any questions, the subject will be asked to sign the consent form if he or she agrees to participate.

### **II. Evaluations of Benefits and Risks/Discomforts**

Each subject will be given a medical and psychiatric evaluation. Subjects who receive active treatment may experience greater improvement or possible remission of their mood disorder, as well as improved biomarker

levels and arterial compliance as measured by PWA. To compensate for time spent and inconvenience experienced during the study, a predetermined compensation fee will be given.

Physical risks to subjects are minimal. Discomfort may result from the blood drawing. There may be bruising at the needle site. Certain individuals may feel light-headed during venipuncture. Venipuncture will be performed when the subjects are sitting or recumbent to avoid injury. Discomfort may be experienced due to tedious questionnaires and interviews.

Side effects listed in the Physician's Desk Reference for albuterol include hoarseness, headache, tremors, and palpitations. A hypersensitivity reaction to the drug has been reported in very rare cases. To avoid this risk, subjects will be asked if they have had previous exposure to albuterol, and if they displayed a hypersensitivity reaction. If any adverse reactions are noted after the first administration, the subject will receive no further exposure to the drug.

Discontinuation of subjects' current antidepressant medication is unlikely to lead to worsening of depression or suicidal thoughts because eligible participants are only those who are already depressed whose depression has not responded despite attempts to treat depressive symptoms with antidepressant medication. Subjects will be seen one week after beginning the wash-out phase and one week after beginning the placebo run-in, allowing study staff to frequently assess the subjects' mental status while not on any antidepressant therapy in the unlikely event that subjects begin to feel more depressed or suicidal. Subjects will also be encouraged to contact study staff throughout the duration of the study if they notice any changes in their mental or physical health. If in the opinion of the investigator the patient develops serious suicide risks, the patient will be withdrawn from the study and provided treatment as appropriate. Should this occur the subject will be responsible for the costs of treatment.

### **III. Adequacy of Protection Against Risks**

The rights to privacy for participation in this research and safety of confidential information are paramount. These rights will firstly be protected through coding of data and storage of research records in a locked room. Records that contain identifiable subject information will be stored either in locked cabinets or on a locked computer in secure electronic files. These records will be kept confidential to the fullest extent permitted by law.

## **OTHER STUDY DRUG CONSIDERATIONS**

### **I. Safety Issues of Celecoxib and SSRIs**

There are potential risks associated with taking escitalopram. The most commonly reported side effects of escitalopram are dizziness, drowsiness, and light-headedness. Less commonly reported side effects include: headache, dry mouth, constipation, change in appetite, sweating, palpitations, upset stomach, abdominal pain, weight gain, dyslipidemia, insulin resistance, muscle twitching, and abnormal movements of the face. At the doses we are using, most of the side effects experienced by patients taking escitalopram should be mild to moderate and go away with continued treatment.

Celecoxib is the only coxib available in the US, but carries a FDA-mandated black-box warning for increased cardiovascular risk. The FDA issued this warning based on numerous observational studies and randomized clinical trials on cardiovascular risks associated with all COX-2 inhibitors, but the degree of this risk varies substantially among the different COX-2 inhibitors. Rofecoxib was removed from the market several years ago,

but celecoxib only received a black box warning. Celecoxib is still used widely because it appears at least as safe as other marketed NSAIDs. The full explanation of why celecoxib appears to be safe while other COX-2 inhibitors are not is an area of active research. A review of the literature shows this may relate to the fact that celecoxib possesses a number of artery-positive off-setting affinities compared to rofecoxib, a more pure COX-2 inhibitor. Whatever the reason, celecoxib appears safe at the dose regimen we will prescribe.

## II. Co-Prescription of Celecoxib and Escitalopram at Loyola Medical Center in 2009

[figure not shown]
There is no evidence that celecoxib and escitalopram interact in any way. As far as we know, their biomolecular targets (COX-2 and serotonin transporter) do not have shared affinities. Escitalopram has low potential for clinically significant interactions. Studies *in vitro* have shown that the biotransformation of escitalopram to its demethylated metabolites depends on three parallel pathways (cytochrome P450 (CYP) 2C19, 3A4 and 2D6). Celecoxib, on the other hand, is metabolized by 2D6. Nevertheless, since we know it is common practice to combine celecoxib with antidepressants, mostly in non-psychiatric settings, we conducted an internal review of all prescriptions of celecoxib in combination with an antidepressant throughout Loyola Medical Center during 2009. The results are presented in summary form below. As shown, escitalopram represented 19.2 % of all prescriptions of an antidepressant co-prescribed with celecoxib. No adverse events were recorded in a total of 224 cases receiving the combination at our institution.

Situations Resulting in Combination	No. Cases	Serious Adverse Events from Combo
Primary treatment of mood disorder	21	0
Primary treatment was the antidepressant for other than mood disorder	17	0
Primary treatment for pain (2 nd depression?)	28	0
Post-surgery	6	0
Cardiovascular disease present	38	0
GI disease present	10	0
Reason unspecified for combination treatment	104	0
Total	224*	0

\*Of all the incidents of antidepressant co-prescriptions with celecoxib in 2009, escitalopram was the agent co-prescribed 19.2 % of the time. There were no serious adverse events reported due to any antidepressant in combination with celecoxib at Loyola Medical Center in 2009.

NSAIDs are known to carry a risk of gastrointestinal bleeding. However, this is mostly a property of COX-1 inhibitors. Escitalopram may also impose a minor risk of prolonged bleeding through its platelet serotonin depletion property. Because of this property, we will monitor platelets during treatment. However, the risk of bleeding appears very low when the odds ratios published in a recent review article is considered (Loke 2008). The odds ratios of gastrointestinal bleeding were summarized from all prior studies of SSRIs alone, NSAIDs alone, and SSRIs + NSAIDs. A meta-analysis was performed on published papers representing a total of 153,000 patients. The article also obtained 161 potentially relevant private company reports covering four SSRIs – fluoxetine, paroxetine, sertraline, and escitalopram – in regard to adverse event frequencies involving GI hemorrhage. The article also assembled all post-marketing reports of adverse events submitted to the FDA or to the Canadian Adverse Events Database. From this large database they concluded that the odds ratio of developing GI bleeding from an SSRI alone was 2.36. By comparison, the odds ratio of developing GI bleeding from an NSAID alone was 3.16. Finally, the odds ratio of developing GI bleeding from concomitant use of an

SSRI and an NSAID was 6.33. However, it is important to realize this was for *all* NSAIDs combined. COX-2 inhibitors were found to be involved in only a fraction of the total NSAID+SSRI adverse event cases producing GI bleeding. A much lower rate of bleeding risk is expected in our study because the median ages and durations of treatment in the review exceed those of the Loke review (median age 66 years, median length of drug exposure 25 weeks). Also, the studies assembled were not limited to the 400 mg/d dose of celecoxib we will prescribe. Therefore, developing a bleeding diathesis from the combination treatment should be very low: we estimate no more than 1 per 350 cases.

The above graph compiled by the Risk Communicator Institute illustrates the very low risk celecoxib poses for GI bleed or heart attack compared to other agents. It is directly comparable to that of naproxen and lower than that of ibuprofen, both of which are sold without prescription.

Another potential risk to subjects concerns confidential information. It will be explained that our study is not designed to produce confidential data of any kind that presents any known risk to the subjects. However, it will be acknowledged in plain language that we cannot guarantee that in some unpredictable way either their background information or the samples could become a future liability.

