## DATA ANALYSIS AND STATISTICAL METHODS

### I. Statistical Analysis

Specific Aim 1 is to determine if combined pharmacotherapy of escitalopram + celecoxib will result in earlier and/or improved affective responses compared to escitalopram + PBO. Additionally, Specific Aim 1 seeks to control for pain perception in this analysis. For this aim, the patients in the two treatment arms will be compared on HAM-D, HAM-A, MADRS, BDI, and BAI scores. This will be accomplished with an analysis of covariance conducted at weeks 1, 2, 4 and 8. Baseline mood scores and McGill Pain Inventory scores will be used as covariates. In addition, the number of patients who are and are not classified as remitters at week 8 (those having a HAM-D score of 7 or less) will be tallied and cross-referenced with treatment group (escitalopram + celecoxib or escitalopram + PBO). The frequencies in the resulting 2-by-2 contingency table will be analyzed with the Pearson Chi-Square Test for Association.

For Specific Aim 2, dealing with treatment safety and tolerability, the numbers of patients who do and do not experience adverse events at weeks 1, 2, 4, and 8 will be tallied and cross-referenced with treatment group. The frequencies in the resulting 2-by-2 contingency table will be analyzed with the Pearson Chi-Square Test for Association. Additionally, to understand whether any pharmacodynamic interaction exists between escitalopram and celecoxib, blood levels of escitalopram and celecoxib drawn at weeks 4 and 8 will be compared for patients in the two treatment groups with an analysis of covariance using baseline levels as a covariate. If there is no pharmacokinetic interaction then we expect that there will be no statistically significant results for these analyses.

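### Specific Aim 2 asks about gastrointestinal bleeding and cardiovascular safety, but the only adverse-event test stated pools events of every kind; the background bleeding figures also need a shown basis and a clear denominator

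*Combined protocol and SAP*

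**What the plan says.** **Aim and analysis.** Specific Aim 2 (Hypotheses and Specific Aims) asks, among other things, whether the combination raises safety problems, and it names gastrointestinal bleeding and cardiovascular health. For this, Data Analysis and Statistical Methods, I. Statistical Analysis, states that "the numbers of patients who do and do not experience adverse events at weeks 1, 2, 4, and 8 will be tallied". The counts are crossed with treatment group in a 2-by-2 table and tested with Pearson's chi-square. No other adverse-event analysis is given. Study Endpoints, III, classes safety as exploratory and unpowered.

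**Data collected.** The Schedule of Events has the GI event inventory (CSULGIE) at screening, baseline and every later visit, and CBC, PT and PTT at screening and weeks 2, 4 and 8. Brachial blood pressure is taken at the SphygmoCor sessions (baseline, weeks 4 and 8).

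**Background evidence.** Other Study Drug Considerations, II, says of its hospital data that "we conducted an internal review of all prescriptions of celecoxib in combination with an antidepressant throughout Loyola Medical Center during 2009". The text then reports: "No adverse events were recorded in a total of 224 cases receiving the combination at our institution". The table column counts serious adverse events. The footnote to 224 says "escitalopram was the agent co-prescribed 19.2 % of the time" and "There were no serious adverse events reported due to any antidepressant in combination with celecoxib at Loyola Medical Center in 2009".

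**Bleeding figure.** The same section cites odds ratios for GI bleeding of 2.36 (SSRI alone) and 3.16 (NSAID alone). For the two together, it says the odds ratio with an "SSRI and an NSAID was 6.33". After arguing that age, duration and dose make the risk lower here, it concludes for bleeding diathesis that "we estimate no more than 1 per 350 cases".

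**The concern.** The aim asks a specific question and the stated analysis answers a different one. In an any-event table, a patient with a GI bleed and a patient with a headache count the same, so the result carries almost no information on bleeding or cardiovascular harm. It is also unclear whether there is one table per visit or one overall, and neither is described as cumulative incidence per patient. The protocol itself recognises that an SSRI with a COX-2 inhibitor might promote bleeding, and it collects the data needed to describe this. The stated analysis would leave that part of Aim 2 unanswered.

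The background section adds to the problem. It gives the only absolute bleeding risk in the text, and a reader cannot see where it comes from. The hospital data beside it are described in two ways that do not agree on the type of event and may not agree on the denominator.

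**Working it through.** **1. What the trial could say about a rare event.** With zero events in n patients, the exact one-sided 95% upper limit is 1 − 0.05^(1/n); the upper end of a two-sided exact 95% interval is 1 − 0.025^(1/n). The confidence level is my assumption, since the plan gives none for safety rates.

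Arm size: Determination of Sample Size gives 45 completers per group. Study Design plans 70 randomised at the main site and about 30 in Munich, so (70 + 30)/2 = 50 treated per arm.

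| Zero events in | One-sided limit | Two-sided limit |
|---|---|---|
| 45 | 6.4% | 7.9% |
| 50 | 5.8% | 7.1% |

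If the true risk were 1/350, the chance of seeing at least one event in the combination arm is 1 − (349/350)^n, which is 12% at n = 45 and 13% at n = 50.

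**2. Chi-square for such events.** At 1/350 the expected count in an arm of 50 is 50/350 = 0.14. Under the usual rule of thumb of an expected count of 5 per cell, the pooled rate would have to be 5/50 = 10%. Exact methods are therefore needed once the named events are separated out.

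**3. Can 1 per 350 be reproduced?** No. The text gives only odds ratios, and an absolute risk also needs a baseline: odds = OR × baseline odds. Solving backwards with 6.33, a risk of 1/350 has odds 1/349, so the baseline odds are (1/349)/6.33, a baseline risk of about 1 in 2,210. The text gives no such value. For assumed baselines:

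| Assumed baseline | Risk at OR 6.33 |
|---|---|
| 1/500 | 1 in 80 |
| 1/1,000 | 1 in 159 |
| 1/2,000 | 1 in 317 |
| 1/5,000 | 1 in 791 |
| 1/10,000 | 1 in 1,581 |

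These fall on both sides of 1/350. The odds ratios also concern GI bleeding, whereas the estimate is for bleeding diathesis. The sentence that should link them says ages and durations in the review exceed those of that same review, so as printed it compares the review with itself.

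**4. The hospital count.** The rows reproduce the total: 21 + 17 + 28 + 6 + 38 + 10 + 104 = 224.

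- If the 224 are celecoxib with any antidepressant, which is the natural reading of the stated scope, escitalopram cases number 0.192 × 224 = 43.0. Zero in 43 allows up to 6.7% (two-sided 8.2%).
- If all 224 had escitalopram, zero in 224 allows up to 1.33%, or 1 in 75 (two-sided 1.63%).

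Both limits apply to serious adverse events, because that is what the table and footnote count. They say nothing about bleeding that was not classed as serious.

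**The case against.** **Acknowledged and partly handled.** The plan concedes that safety is exploratory and unpowered. Safety Assessments and Adverse Events Monitoring records clinically significant worsening from the entry examination as an adverse event, so a marked hematocrit fall or blood-pressure rise can enter the any-event table. Suspension and termination criteria and safety-board reporting also exist. All of this stands: harm is being watched for. It does not supply a bleeding-specific or cardiovascular summary by arm, and low power is a reason to report intervals.

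**Stronger readings the documents do not support.**

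- A reader might infer that 1 per 350 was computed from the 224 cases, or that the trial is meant to confirm it. The text says neither; it offers the figure as an expectation from the cited review, age, duration and dose. Zero events in 1,048 patients would be needed to exclude a higher risk (one-sided 95%), but the plan makes no such claim.
- A reader might tie the figure to the statement under Evaluations of Benefits and Risks/Discomforts that physical risks are minimal. That paragraph concerns blood drawing and questionnaires and does not cite the figure.
- A reader might conclude that no baseline rate exists. The section refers to a graph that is absent from the text available here. It is described as comparing celecoxib with other agents for GI bleeding and heart attack, and its content cannot be checked. Only the absence of a derivation in the text can be stated.
- A reader might take 43 as established. It is an inference. The section heading names escitalopram, and the text speaks of 224 cases on the combination. If those are all escitalopram cases, the implied any-antidepressant total is 224/0.192 ≈ 1,167, and zero events there would give a limit of 1 in 390 (two-sided 1 in 317). That total is nowhere stated and is not specific to escitalopram.

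The self-comparing sentence is an evident slip: the review's median age of 66 and 25 weeks of exposure are set against ages 18 to 65 and 8 weeks here. Correcting it is editorial.

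**Conclusion.** The point holds for the analysis of Aim 2. The stated test does not isolate the events the aim names, and the trial can exclude only rates above about 6% if none occurs (6.4% at 45, 5.8% at 50, one-sided 95%; 7.9% and 7.1% as two-sided limits). This assumes 45 to 50 treated combination patients and complete ascertainment.

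The background wording is a lesser, supporting matter. The 1-per-350 figure is not shown to be wrong; it is simply not derivable from the text. The event type is inconsistent, and the denominator is ambiguous between about 43 and 224 escitalopram cases. Nothing here affects the efficacy endpoints, sample size or eligibility.

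**What to change.** 1. **I. Statistical Analysis, Specific Aim 2.** Add the cumulative per-patient incidence, by arm, of GI/bleeding events (CSULGIE events, hematocrit fall, PT/PTT abnormality) and of raised blood pressure, with exact 95% confidence intervals. Define each event in advance. Use all treated patients as the denominator and say so, because the plan's intent-to-treat set requires at least one week on active medication. State that zero events in about 45 to 50 combination patients excludes only rates above about 6%.
2. **Other Study Drug Considerations, II, bleeding estimate.** Show the baseline rate and calculation behind 1 per 350, or delete the figure. Correct the sentence that compares the review with itself.
3. **Same section, hospital review.** Reconcile the text on adverse events with the table's serious adverse events. State whether the 224 cases are celecoxib with any antidepressant or with escitalopram only, and give the escitalopram count with its upper limit.

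Cost: a few table rows from data already collected, some rewording, and a less favourable safety statement. No design change is needed.
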